#### 9.4 Demographic and Baseline Characteristics

The following demographic, baseline characteristics, baseline disease characteristics and baseline and prior medications of interest will be summarized descriptively by randomized treatment group.

##### **Demographics:**

- Age (years)
- Age groups ( $\geq 18$  to  $< 50$ ,  $\geq 50$  and  $18 - 64$ ,  $65 - 74$ ,  $75 - 84$ )
- Sex (male, female)
- Race (American Indian or Alaska, Native Asian, Black or African American, Native Hawaiian or Other Pacific Islander, White, Other)
- Ethnicity (Hispanic or Latino, Not Hispanic or Latino)
- Geographic region (Eastern Europe, Asia Pacific, Rest of World)

##### **Baseline Characteristics:**

- Height (cm)
- Weight (kg)
- Body Mass Index (BMI) ( $\text{kg}/\text{m}^2$ )

##### **Baseline Disease Characteristics:**

- Modified Mayo score at baseline
- Total Mayo score at baseline
- Individual Mayo subscores at baseline
- **Partial Mayo score**
- Disease localization (proctosigmoiditis, left-sided colitis, extensive colitis, pancolitis)
- Duration of UC (years from date of diagnosis to first dose date)
- Fecal calprotectin

##### **Baseline medications:**

- Oral 5-aminosalicylates (5-ASA)
- Corticosteroid
- Immunomodulator (azathioprine, 6-mercaptopurine, methotrexate)

##### **Prior medication history:**

- Prior experience, including reason for stopping, for the following medication classes:
  - conventional therapies (azathioprine, 6-mercaptopurine, methotrexate, corticosteroids)

- biologic therapy (including number of prior biologic therapy classes and total number of prior biologics)
- anti-TNF therapy
- targeted small molecule therapy (ie. Janus kinase [JAK] inhibitor)

## 9.5 Efficacy Analyses

The efficacy analyses are summarized in [Table 9-1](#), [Table 9-2](#), [Table 9-3](#) and [Table 9-4](#) and analyses of efficacy endpoints are described from Section 9.5.1 to Section 9.5.4.

**Table 9-1. Primary Efficacy Estimand Summary Table**

Endpoint	Primary Summary and Analysis Method - FAS	Additional Analysis
Clinical remission at week 12	Logistic regression model described in 9.5.1.1 Composite variable intercurrent event strategy	Treatment policy intercurrent event strategy

**Table 9-2. Secondary Efficacy Endpoint Summary Table**

Endpoint	Primary Summary and Analysis Method - FAS
Clinical response at week 12	Logistic regression model described in 9.5.1.1
Endoscopic remission at week 12	Composite variable intercurrent event strategy
Symptomatic remission at week 12	
Combined endoscopic remission and histologic remission of the colon tissue at week 12	
Change from baseline in histological score at week 12 as measured by Geboes score	ANCOVA model described in 9.5.1.2 Composite variable intercurrent event strategy

**Table 9-3. Phase 2 Induction Period Exploratory Efficacy Endpoint Summary Table**

Endpoint	Primary Summary and Analysis Method - FAS
Change from baseline in fecal calprotectin at week 12	Repeated measures model described in 9.5.1.3 Composite variable intercurrent event strategy

### 9.5.1 Descriptions of Statistical Models

#### 9.5.1.1 Logistic Regression Model

The logistic regression model will be used to test the difference in rates between each efavaleukin alfa dose and placebo ([Ge et al. 2011](#)). The stratification factors as captured in IRT will be included as covariates.

The estimate of the risk difference between each efavaleukin alfa dose and placebo, the corresponding 2-sided 95% Wald confidence interval, and the p-value obtained from the logistic regression model will be provided.

In case the logistic regression model does not converge due to separation, Firth's modified logistic regression may be used to reduce bias in the parameter estimates [[Heinze and Schemper \(2002\)](#)].

#### **9.5.1.2 ANCOVA Model**

Analysis of covariance (ANCOVA) model will be used to test the difference between each efavaleukin alfa dose and placebo, with stratification factors as captured in IRT as covariates. The least-squares mean estimate of the treatment differences (efavaleukin alfa dose group – placebo) and the corresponding 95% confidence intervals will be summarized.

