9.3.1 Covariates

The impact of baseline covariates on the treatment effect may be explored and adjusted in the model for the primary and secondary endpoints as deemed necessary.

The baseline covariates include, but are not limited to the following:

- Stratification factors
 - Prior experience with at least 1 biologic or targeted small molecule: (yes, no)
 - Corticosteroid use at randomization: (yes, no)
- Age (< 40 years, \geq 40 years)
- Sex (female, male)
- Race (white, non-white)
- Geographic region (Eastern Europe, Asia Pacific, Rest of World)
- Mayo score at baseline
- Disease localization (proctosigmoiditis, left-sided colitis, extensive colitis, pancolitis)
- Duration of UC (years from date of diagnosis to first dose date)

Stratification factors will be included as covariates in the model. If included as covariates in the model for treatment comparisons, the IRT value will be used to be consistent with the randomization scheme.

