9.4.2.2 Efficacy Analyses

Endpoint/ Estimand	Statistical Analysis Methods
Primary	Logistic regression will be performed to test the difference in clinical remission rates between each efavaleukin alfa dose and placebo (Ge et al, 2011). The stratification factors as captured in IRT will be included as covariates. The estimate of the risk difference between each efavaleukin alfa dose and placebo, the corresponding 2-sided 95% Wald confidence interval, and the p-value obtained from the logistic regression model will be provided. Missing primary endpoint data will be imputed using nonresponder imputation.
Secondary	Clinical response, endoscopic remission, and combined endoscopic and histologic remission will be analyzed using the same methods as the primary estimand. Change from baseline in histologic score at week 12 will be analyzed

	using an ANCOVA model with the stratification factors as capture in IRT as covariates.
Exploratory	Will be described in the statistical analysis plan finalized before database lock

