### 3.3 Adaptive Design

Interim analyses will be conducted to assess for futility. [REDACTED]

[REDACTED]. Futility will be assessed at each interim.  
[\(Section 7.1\).](#)

The interim analyses will be conducted by an external Independent Biostatistics Group (IBG) and results evaluated by an independent DMC. In the case where pre specified decision rules are met at a planned interim analysis, a Data Access Plan (DAP) Team will be invoked. The DAP Team is comprised of a small team of senior members internal to Amgen but external to the study team. To facilitate final decision making, the DAP Team may evaluate unblinded results. Further details will be described in a Data Access Plan.

The study team, investigators and subjects will remain blinded to the results of the IAs unless the DAP team have made the decision to terminate the trial.

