**5.2 Study Points of Reference**

**Baseline:**

Baseline fecal calprotectin is the last measurement taken on or before the date of the first dose of IP.

Baseline for all other parameters is the last measurement for the endpoint of interest taken before the first dose of IP. If the measurement is taken on the same day as the first dose and the exact measurement time relative to the first dose is unknown, it will be assumed to have been taken prior to the first dose of IP.

If a subject did not receive IP, baseline is the closest recorded measurement on or prior to the randomization date for all parameters.

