**Worst Case Imputation:**

Worst case imputation will be used for missing postbaseline values for Geboes score, total Mayo score, partial Mayo score, and individual Mayo subscores. **In other words**, missing postbaseline values at any visit will be imputed using the highest score observed across baseline and all postbaseline visits.

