#### **9.5.1.3 Repeated Measures Model**

The repeated measures model will be used to test the difference between each efavaleukin alfa dose and placebo at each scheduled visit. The model will include terms for treatment group, stratification factors (from IRT), scheduled visit, and the interaction of treatment with scheduled visit. The least-squares mean estimate of the treatment differences (efavaleukin alfa dose group – placebo) and the corresponding 95% confidence intervals will be summarized for each scheduled visit.

To account for repeated measurements within a subject across the visits, the model will use an unstructured covariance.

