#### **9.5.3 Analyses of Secondary Efficacy Endpoint(s)**

The logistic regression model described in [Section 9.5.1.1](#) will be used to test the difference in rates between each efavaleukin alfa dose and placebo for the following secondary endpoints:

- Clinical response at week 12
- Endoscopic remission at week 12
- Symptomatic remission at week 12
- Combined endoscopic and histologic remission of the colon tissue at week 12

Subjects with missing data will be imputed using nonresponder imputation. The same incurrent event composite variable strategy as used for the primary estimand will be used for these secondary endpoints.

Change from baseline in histological score at week 12 as measured by Geboes score will be analyzed using an analysis of covariance (ANCOVA) model described in [Section 9.5.1.2](#). Subjects with missing week 12 Geboes score, or who experience any of the intercurrent events described in [Section 9.5.2](#) will be imputed using worst case imputation.

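### The models for change in Geboes score and change in fecal calprotectin omit the outcome's baseline value, so they may be less precise than the collected data allow

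*SAP*

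**What the plan says.** The secondary histology endpoint in SAP 9.5.3 is "Change from baseline in histological score at week 12 as measured by Geboes score". SAP 9.5.1.2 fits it by ANCOVA "with stratification factors as captured in IRT as covariates", and protocol 9.4.2.2 agrees: "using an ANCOVA model with the stratification factors as capture in IRT as covariates". The exploratory calprotectin endpoint is a change from baseline analysed by repeated measures, and SAP 9.5.1.3 lists its terms: "The model will include terms for treatment group, stratification factors (from IRT), scheduled visit, and the interaction of treatment with scheduled visit". SAP 5.4 defines change as the plain difference from baseline.

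Both baselines exist. The schedule of activities places a histology biopsy at screening and a calprotectin sample at day 1. SAP 5.2 defines the calprotectin baseline ("Baseline fecal calprotectin is the last measurement taken on or before the date of the first dose of IP") and has a general rule that covers Geboes.

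No other section restores the term. Protocol 9.3.1 says the impact of baseline covariates "may be explored and adjusted in the model for the primary and secondary endpoints as deemed necessary". That is optional and covers primary and secondary endpoints only. Its list is open-ended, but it names neither baseline Geboes nor baseline calprotectin. SAP 4.1 names only the stratification factors, and only for the primary endpoint. The SAP revision history records that covariate analyses were taken out in Amendment 2.

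**The concern.** Analysing a change score without its baseline fixes the slope of week 12 on baseline at 1. Adjusting for baseline lets the data estimate that slope. When the true slope is not 1, chance baseline differences between arms pass into the treatment contrast as avoidable variance. The two binary strata remove only the part of baseline variation related to prior biologic or small-molecule use and to corticosteroid use.

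What is at stake is the width of the reported 95% intervals, and the nominal p-values, for one secondary and one exploratory endpoint. Bias is not at issue, and the primary endpoint is untouched.

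**Working it through.** **Inputs.** Four arms of 60, 240 in total (protocol 4.1.1), and the model terms listed in SAP 9.5.1.2 and 9.5.1.3. The documents state no figure to reproduce here: the sample-size rationale is blacked out, and the legible text gives no SD or correlation for either outcome. Two quantities are therefore assumed and varied: *r*, the within-stratum correlation between baseline and week 12, and *k*, the week 12 SD divided by the baseline SD.

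**Closed form.** Set the baseline SD to 1.
- Change score, no baseline term: variance = 1 + k² − 2rk.
- Baseline-adjusted: variance = k²(1 − r²).
- Difference = (1 − rk)². It is never negative, and is zero only when the slope rk equals 1.

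The interval shrinks by 1 − √ratio, where ratio = adjusted/unadjusted.

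| k | r = 0.3 | r = 0.5 | r = 0.7 | Interval narrower by |
|---|---|---|---|---|
| 1 | 0.91/1.40 = 0.65 | 0.75/1.00 = 0.75 | 0.51/0.60 = 0.85 | 19%, 13%, 8% |
| 1/0.7 | 1.857/2.184 = 0.850 | 1.531/1.612 = 0.949 | 1.041/1.041 = 1.000 | 8%, 3%, 0% |
| 0.7 | 0.446/1.07 = 0.417 | 0.3675/0.79 = 0.465 | 0.250/0.51 = 0.490 | 35%, 32%, 30% |

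In power terms with k = 1: an effect detectable with 80% power after adjustment (60 per arm, two-sided 0.05) has 62%, 68% and 73% power in the planned model at r = 0.3, 0.5 and 0.7.

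**Worst-case imputation for Geboes.** SAP 5.5 says "missing postbaseline values at any visit will be imputed using the highest score observed across baseline and all postbaseline visits". Where baseline is the highest score, the imputed change is zero, and this weakens the gain. Let a share p of changes be zero independently of baseline, with mean change μ otherwise:

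ratio = 1 − [(1 − p)(rk − 1)]² / [(1 − p)·Var(change) + p(1 − p)μ²]

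Take p = 0.2 and μ = −1 baseline SD:
- k = 1: 1 − 0.3136/1.28 = 0.755; 1 − 0.16/0.96 = 0.833; 1 − 0.0576/0.64 = 0.910.
- k = 1/0.7: 0.890, 0.964, 1.000.

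A separate single-visit simulation (four arms of 60, two strata, equal SDs, 25% of week 12 values replaced by the higher of the two scores) gave model-based variance ratios of 0.65, 0.78 and 0.92 at r = 0.2, 0.5 and 0.8.

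**Repeated measures for calprotectin.** The unstructured covariance does not recover the baseline information, because the response is already a change and baseline is not a modelled response. A simulation compared the model with and without baseline-by-visit: 2000 trials per setting, four arms of 60, three post-baseline visits, complete data, assumed correlation of 0.6 between follow-up visits. Variance ratios for the week 12 contrast at r = 0.3, 0.5 and 0.7 were:
- k = 1: 0.684, 0.731, 0.842.
- k = 1/0.7: 0.866, 0.941, 1.001.

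The mean estimate was within 0.01 of the true value of zero in both models.

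**Cost of the extra term.** About 1 + 1/232 = 1.004, or 0.4% of variance, at 240 subjects. The number analysed is not given.

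**The case against.** The strongest reply is that this is a preference. The estimates are not biased by the omission, the endpoints carry nominal p-values without multiplicity adjustment, the trial has already stopped for futility, and the documents tie no decision to these interval widths. This stands as a limit on importance.

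The size also rests wholly on assumed values of r and k. The equal-SD figures have no better support than the others, and one plausible setting shows no gain at all. When the slope is exactly 1, the planned model is better by the 0.4% above. The calprotectin simulation used complete data, whereas SAP Table 9-3 applies a composite strategy for which the SAP gives no calprotectin imputation rule. Its ratios, and its showing of no bias, are therefore illustrations and not this trial's loss. All of this stands, and none of it shows that the planned models are materially more precise in any setting.

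Protocol 9.3.1 could be read as already permitting baseline Geboes, since its list is open. But it is optional, does not reach the exploratory calprotectin endpoint, and the current SAP does not take it up.

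Finally, timing. The SAP is dated 19FEB2025, after the August 2024 futility result. SAP 3.3 keeps the study team blinded to interim results "unless the DAP team have made the decision to terminate the trial", while SAP 7.1 states no such exception. Replacing the models now could be post hoc, and the fix has to allow for that.

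**Conclusion.** The concern holds. Both change-score models leave out a baseline value that the trial collects. Apart from the trivial cost of one extra term, they are never more precise than the adjusted models, and they are less precise unless the within-stratum slope of week 12 on baseline is 1.

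The loss cannot be fixed from the documents. If week 12 values vary at least as much as baseline values, the calculations above put the gain between 0% and 19% of interval width before imputation. It would be larger if baseline varies more than week 12. Because entry selects active disease, baseline spread may be compressed, so the smaller gains deserve weight. Worst-case imputation reduces the Geboes gain further. The calculations assume a common slope across arms. This is a low-cost improvement to consider, not an error that changes a conclusion.

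**What to change.** First state whether the study team was still blinded to treatment-level results when the model choice is made.

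- If still blinded: add baseline Geboes score to the ANCOVA in SAP 9.5.1.2, and add baseline fecal calprotectin and baseline-by-visit to the model in SAP 9.5.1.3. Align protocol 9.4.2.2, which names the same covariates for Geboes, or record the departure in SAP Section 11.
- If already unblinded: keep both models as written and report the baseline-adjusted versions beside them, declared as additional analyses.

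The cost is one model term for Geboes, two for calprotectin, a documentation entry and the statement on blinding. No new data are needed.

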#### **9.5.1.3 Repeated Measures Model**

The repeated measures model will be used to test the difference between each efavaleukin alfa dose and placebo at each scheduled visit. The model will include terms for treatment group, stratification factors (from IRT), scheduled visit, and the interaction of treatment with scheduled visit. The least-squares mean estimate of the treatment differences (efavaleukin alfa dose group – placebo) and the corresponding 95% confidence intervals will be summarized for each scheduled visit.

To account for repeated measurements within a subject across the visits, the model will use an unstructured covariance.

#### **9.5.2 Analyses of Primary Efficacy Endpoint(s)/Estimand(s)**

The primary analysis of the primary efficacy estimand will use the logistic regression model described in [Section 9.5.1.1](#) based on the Full Analysis Set (FAS) described in [Section 6.1](#) and the subjects with missing data will be imputed using nonresponder imputation.

A composite variable strategy will be used to handle intercurrent events for the primary estimand. Subjects will be considered as not meeting the endpoint if they meet any of the following criteria:

- Initiation of or **increase the dose of UC related** protocol-prohibited medication or concomitant UC medication **between the date of the screening endoscopy and the week 12 endoscopy**
- **UC related protocol-prohibited medications include:**
  - **Any investigational therapy for Ulcerative Colitis**

- **Biologic agents (eg, Vedolizumab, Ustekinumab, Infliximab, Adalimumab, Golimumab)**
- **T cell depleting agents (eg, Antithymocyte immunoglobulin, Campath [Alemtuzumab])**
- **Recombinant IL-2 (eg, Proleukin [aldesleukin])**
- **Jak Inhibitors (eg, Baricitinib, Tofacitinib, Upadacitinib)**
- **Other immunomodulatory agents (eg, S1P modulators [Fingolimod and siponimod], cyclosporine, Mycophenolic acid, tacrolimus, sirolimus)**
- **Corticosteroids via IV, intramuscular, or rectal route**
- **5-ASAs via rectal route**
- **Concomitant UC medication includes:**
  - **Oral 5-ASA**
  - **Immunomodulators (azathioprine, 6-mercaptopurine, methotrexate)**
  - **Oral corticosteroids**
- Discontinuation of investigational product on or prior to the **end of the induction period**

To assess the impact of the composite variable strategy for the intercurrent events, an additional analysis will be performed using the treatment policy strategy. In this analysis the actual remission status at week 12 will be used, regardless of each intercurrent event. Subjects with missing week 12 remission status will be imputed using nonresponder imputation.

#### **9.5.3 Analyses of Secondary Efficacy Endpoint(s)**

The logistic regression model described in [Section 9.5.1.1](#) will be used to test the difference in rates between each efavaleukin alfa dose and placebo for the following secondary endpoints:

- Clinical response at week 12
- Endoscopic remission at week 12
- Symptomatic remission at week 12
- Combined endoscopic and histologic remission of the colon tissue at week 12

Subjects with missing data will be imputed using nonresponder imputation. The same incurrent event composite variable strategy as used for the primary estimand will be used for these secondary endpoints.

Change from baseline in histological score at week 12 as measured by Geboes score will be analyzed using an analysis of covariance (ANCOVA) model described in [Section 9.5.1.2](#). Subjects with missing week 12 Geboes score, or who experience any of the intercurrent events described in [Section 9.5.2](#) will be imputed using worst case imputation.

#### **9.5.4 Analyses of Exploratory Efficacy Endpoint(s)**

##### **9.5.4.1 Phase 2 Induction Period Analyses of Exploratory Efficacy Endpoint**

The repeated measures model described in [Section 9.5.1.3](#) will be used to assess the difference between each efavaleukin alfa dose and placebo at each scheduled visit through week 12 for the following exploratory endpoints:

- Change from baseline in fecal calprotectin at week 12

##### **9.5.4.2 Long-Term Treatment Period Analyses of Exploratory Efficacy Endpoint**

Analysis of the long-term treatment period exploratory efficacy endpoints will use the long-term treatment period efficacy analysis set. Summary statistics will be used to summarize all long-term treatment period exploratory endpoints.

**The same intercurrent event composite variable strategy as used for the primary estimand will be used for these exploratory endpoints.**

#### **9.6 Safety Analyses**

##### **9.6.1 Adverse Events**

The Medical Dictionary for Regulatory Activities (MedDRA) version 27.0 or later will be used to code all events categorized as adverse events to a system organ class and a preferred term. The severity of each adverse event will be graded using CTCAE criteria version 5.0 or later ([Appendix A](#)). Summaries of adverse events during the induction adverse event exposure period will be presented by actual treatment received in the induction period. Exposure-adjusted subject incidence rates for the overall study period will be presented by actual treatment received in the overall study.

Subject incidence of all TEAEs, serious TEAEs, TEAEs leading to discontinuation from investigational product, fatal TEAEs, treatment-related TEAEs, treatment-related serious TEAEs, treatment-related TEAEs leading to discontinuation from investigational product,

treatment-related fatal TEAEs, and TEAEs of interest that occur in the induction adverse event exposure period will be summarized.

Subject incidence of treatment-emergent adverse events identified by COVID-19 standardized MedDRA queries and serious adverse events occurring on or after the COVID-19 infection that occur in the induction adverse event exposure period will also be summarized.

Subject incidence of events of interest (standardized MedDRA queries and/or Amgen Medical Queries) that occur in the induction adverse event exposure period will also be summarized according to their categories and preferred term. Events of interest could include but are not limited to Hypersensitivity, Tachyarrhythmias, Tachypnea, Hematopoietic Cytopenia, Drug Reaction with Eosinophilia, Leucocyte Changes, Infection and Infestation, Cytokine Release Syndrome, and Injection Site Reaction. Number of episodes and duration of treatment-emergent injection site reactions will be further summarized by treatment group.

In addition, summaries of TEAEs and serious TEAEs occurring in at least 5% of the subjects in any treatment arm and serious TEAEs occurring in at least 2% of the subjects in any treatment arm by preferred term that occur in the induction adverse event exposure period will be provided in descending order of frequency.

Summaries of TEAEs and serious TEAEs that occur in the induction adverse event exposure period will be tabulated by system organ class, preferred term, and grade. An overall summary of adverse events by toxicity grade will be provided.

Exposure-adjusted subject incidence rate of TEAEs, serious TEAEs, TEAEs leading to discontinuation from investigational product, fatal TEAEs, treatment-related TEAEs, treatment-related serious TEAEs, treatment-related TEAEs leading to discontinuation from investigational product, treatment-related fatal TEAEs, and TEAEs of interest will be presented for the overall study period.

Overall summary of subject incidence of TEAEs and by preferred term and worst severity grade will be provided by anti-AMG592 and Anti-IL-2 antibody status.

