**Treatment-emergent adverse event (TEAE):**

Treatment-emergent adverse events are events categorized as Adverse Events (AEs) starting on or after first dose of IP as determined by “Did event start before first dose of investigational product?” equal to “No” or missing on the Events eCRF and up to the EOS date.

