**Induction Adverse Event Exposure Period:**

Induction adverse event exposure period starts on the date of the first dose of IP up to min[EOS date, study day 90, max(week 12 IP date - 1, week 12 endoscopy date)].

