### **9. Statistical Methods of Analysis**

#### **9.1 General Considerations**

All categorical variables will be summarized using the number and percent of subjects falling into each category and all continuous variables will be summarized using mean, standard deviation (SD), median, first quartile (Q1), third quartile (Q3), minimum, maximum, and number of subjects with observations.

Nominal p-values will be reported for the primary, secondary, and select exploratory efficacy endpoints, with no adjustment for multiplicity.

Safety endpoints will be summarized descriptively, including treatment-emergent adverse events and serious adverse events in the induction period, clinically significant changes in laboratory values and vital signs, and incidence of antidrug antibodies.

Exposure-adjusted treatment-emergent adverse events and serious adverse events will be summarized for the overall study period.

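### By-treatment adverse event tables by system organ class or preferred term stop at induction (day 90 at the latest), and none is planned for the overall study

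*SAP*

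**What the plan says.** SAP 5.1 defines TEAEs as running from first dose to end of study: the start-before-first-dose question must be answered no "or missing on the Events eCRF and up to the EOS date". It separately defines an induction adverse event exposure period, from first dose "up to min[EOS date, study day 90, max(week 12 IP date - 1, week 12 endoscopy date" (closing brackets omitted).

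SAP 9.6.1 contains three by-treatment summaries that name system organ class or preferred term:

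- events of interest, by category and preferred term;
- TEAEs above the 5% threshold and serious TEAEs above the 2% threshold, by preferred term;
- TEAEs and serious TEAEs that "occur in the induction adverse event exposure period will be tabulated by system organ class, preferred term, and grade".

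The first two carry the same induction limit as the third.

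For the whole study, SAP 9.1 says "Exposure-adjusted treatment-emergent adverse events and serious adverse events will be summarized for the overall study period", and SAP 9.6.1 says "Exposure-adjusted subject incidence rates for the overall study period will be presented by actual treatment received in the overall study". The list that follows has eight TEAE categories (all, serious, leading to discontinuation, fatal, and the treatment-related version of each) plus TEAEs of interest. It names neither organ class nor preferred term.

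Protocol 9.4.2.3.1 tabulates the incidence of all TEAEs by organ class and preferred term and states no period. SAP 7.3 keeps long-term safety data in the final analysis. SAP section 11 declares two changes: removal of unnamed exploratory endpoints after futility, and exclusion of one site.

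**The concern.** TEAEs are collected and coded to end of study, yet a programmer who follows SAP 9.6.1 would produce no by-treatment table showing which terms occurred after induction. The overall-study category rates could show more serious or fatal events in one group, but the plan names no by-treatment table identifying the terms behind the difference, unless they are events of interest.

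The group most affected is placebo nonresponders. Under protocol 6.1.1.2 they start efavaleukin alfa at week 12, about when the induction window closes, so nearly all their on-drug events fall outside the term-level tables. At stake is how complete the reported safety record is for a drug with up to 52 weeks of planned dosing.

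**Working it through.** The plan gives no figure to reproduce. The check is a reading of each output in SAP 9.6.1, followed by schedule arithmetic.

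**1. Outputs in SAP 9.6.1**

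| Output | Period | By treatment | Organ class or preferred term |
|---|---|---|---|
| Eight categories plus TEAEs of interest, incidence | Induction | Yes | Not named |
| COVID-19 query events and later serious events | Induction | Yes | Not named |
| Events of interest by category | Induction | Yes | Preferred term |
| 5% and 2% frequency tables | Induction | Yes | Preferred term |
| TEAEs and serious TEAEs by grade | Induction | Yes | Both |
| Toxicity-grade summary | Not stated | Not stated | Not named |
| Injection site reaction episodes and duration | Not stated | Yes | Not named |
| Eight categories plus TEAEs of interest, exposure-adjusted | Overall study | Yes | Not named |
| Worst-grade summary by antibody status | Not stated | No | Preferred term |

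Four outputs name organ class or preferred term. Three are by treatment, and 3 of 3 are limited to induction. The fourth is split by antibody status.

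**2. End of the induction window**

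Formula (SAP 5.1): the earliest of end of study, day 90, and the later of (week 12 dose date − 1) and the week 12 endoscopy date. The week 12 visit is day 85 ± 5, and dosing may follow by up to 3 days (protocol Table 1-2).

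- Endoscopy day 80: window ends day 80 (same-day dose) or day 82 (dose 3 days later).
- Endoscopy day 85: day 85 or day 87.
- Endoscopy day 90: day 90 in both cases, because of the cap.

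**3. Planned time beyond the window**

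- To the week 52 visit (day 365): 365 − 90 = 275 days; 275/365 = 75.3%.
- To the longest planned stay (protocol 4.4: 61 weeks including up to 35 screening days): 61 × 7 − 35 = 392 days; 392 − 90 = 302; 302/392 = 77.0%.

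**4. Placebo nonresponders who switch**

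- Planned on-drug time from a week 12 dose on day 85: 365 − 85 + 1 = 281 days.
- Long-term assignment needs the locally read endoscopy (protocol 4.1.2), so the first active dose is on or after the endoscopy date. The window reaches that dose only if both fall on the same day. Coverage is then 1/281 = 0.4%; otherwise it is zero.

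**5. The overall-study denominator**

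SAP 5.1 sets overall exposure at end of study − first dose date + 1, where first dose means first dose of investigational product, placebo included. For a switcher whose study ends on day 365, that is 365 days, of which 365 − 281 = 84 (84/365 = 23.0%) precede the first efavaleukin alfa dose. The overall treatment groups in SAP 5.1 keep switchers in their own column, but the column mixes placebo and on-drug time and events. Term-level tables built on this denominator would inherit the mixing.

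**The case against.** There is a fair case on the other side.

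- **No proven departure from the protocol.** Protocol 9.4.2.3 lists its safety analyses under the secondary endpoint, and protocol 9.4.1.2 evaluates secondary objectives at the primary analysis, once all subjects have completed week 12 or left. Protocol section 3 classes long-term TEAEs as exploratory. An induction table is a reasonable reading of the secondary objective. This stands as an argument but does not settle the matter: protocol 9.4.2.3.1 refers to all TEAEs without a cut-off, and subjects enrolled early would already have later events when the primary analysis is triggered.
- **Section 11 may cover it.** SAP 2.1 no longer lists the long-term safety objective, and section 11 moves unnamed exploratory endpoints to a supplemental plan. That is consistent with a deliberate removal. But section 11 does not name it, the supplemental plan is not among the documents, and SAP 7.3 still promises long-term safety analysis.
- **Silence is not exclusion.** True: the overall-study rates could be shown by preferred term. However, for induction the SAP gives the same category list and then adds separate sentences for term-level tables. For the overall study it adds no such by-treatment sentence.
- **Later events are not ignored.** The overall-study rates cover them, and the events of interest address several of the risks named in protocol 2.3. Three further sentences state no period: "Number of episodes and duration of treatment-emergent injection site reactions will be further summarized by treatment group"; "An overall summary of adverse events by toxicity grade will be provided"; and "Overall summary of subject incidence of TEAEs and by preferred term and worst severity grade will be provided by anti-AMG592 and Anti-IL-2 antibody status". Laboratory shift tables use the worst on-study value, and the DMC reviews safety. All this stands. None of it is a by-treatment table by organ class or preferred term.
- **Limiting comparative tables to the randomized period is defensible.** It is, and the induction tables should stay. Later groups depend on response and on investigator opinion, which calls for descriptive labelling rather than omission.

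**Conclusion.** The gap is real but bounded. Every by-treatment summary naming organ class or preferred term is limited to induction, and none is planned for the overall study. The omission affects the completeness of the safety record, chiefly for placebo nonresponders switched at week 12. It does not touch the efficacy conclusions.

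The 75% and the 1 in 281 are shares of planned calendar days, assuming dosing to week 52. Continuation was optional, inadequate responders were to be stopped, and the study ended for futility, so actual long-term person-time is unknown.

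A reader might infer three stronger things that the documents do not support:

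- that the SAP breaches the protocol without declaring it: this is arguable either way, as set out above;
- that post-week-12 events go unanalysed: overall-study category rates and events of interest are planned by treatment;
- that three quarters of actual exposure is missing from the tables: the documents give no exposure data.

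**What to change.** Keep the induction window and its tables. Add to SAP 9.6.1 overall-study tables of TEAEs and serious TEAEs by system organ class and preferred term, giving subject incidence and exposure-adjusted rate, by the overall-study actual treatment groups of SAP 5.1.

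For placebo switchers, count events and person-time from the first efavaleukin alfa dose separately from their placebo period. SAP 5.1 already uses that date to define duration of efavaleukin alfa exposure. Footnote that the overall-study groups are not a purely randomized comparison.

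If the sponsor prefers to move these tables to the supplemental plan, section 11 should name that.

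The cost is SAP wording and a rerun of existing table programs on data already collected and coded, with a split at first efavaleukin alfa dose for the switchers. The downside is more output, and descriptive comparisons that are not purely randomized.
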